EGD with Biopsy ^{21, 22}					X		X			X			
Non-serious adverse events ²³		X	X	X	X	X	X	X	X	X	X	X	X
Adverse events of special interest ²⁴		X	X	X	X	X	X	X	X	X	X	X	X
Serious adverse events ²⁵		X	X	X	X	X	X	X	X	X	X	X	X

Table 1 Notes

ADA: Anti-Drug-Antibody

Ext: Extension

PID: Patient identification number

EGD: Esophago-Gastro-Duodenoscopy

IRT: Interactive response technology

PK: Pharmacokinetic

Eos: Eosinophil

IV: Intravenous

PRO: Electronic Patient Reported Outcome (questionnaire)

ET: Early termination

PGIC: Patient Global Impression of Change

- 1) The ET visits should be conducted 28 (± 3), 35 (± 3), 56 (± 3) and 84 (± 3) days after the last dose of study drug or prior to this, if necessary, to ensure compliance with the visit. If only one ET visit is possible, EGD and end-of-study procedures (Day 35 after last dose of study drug) may occur on the same day. If the end-of-study visit occurs more than 35 days after the last dose of study drug, then perform the visit as soon as possible. In this case, the procedures listed under the 28-day post and 35-day post study drug visit will be conducted unless otherwise directed by the Medical Monitor.
- 2) All concomitant medications taken within 30 days of enrolling into AK002-003X will be captured. All medications used during the study for the treatment of infusion related reactions, adverse events, or for the conduct of EGD will be captured.
- 3) Body weight (in kg) will be recorded on all infusion days and on follow-up Days 736, 757, and Day 785 or 35, 56, and 84 days after last dose, if ET or if previous missed infusions were made up. Current body weight, or body weight from 1 day prior will be used to calculate the amount of AK002 to be mixed with NaCl for the appropriate dose to be administered on each infusion day.
- 4) Do not collect if procedure was performed ≤ 45 days prior to Extension Day 1 (as part of the Day 113 assessment for Study AK002-003). Differential cell counts collected on Day 113 for Study AK002-003 will not be unblinded.
- 5) Vital signs including systolic and diastolic blood pressure, pulse, body temperature, and respiratory rate will be taken after the patient has been at rest for ≥ 5 minutes and before any blood draw. Vital signs will be measured on all dosing days pre-dose, 15 minutes (± 5 minutes) after the start of infusion, and immediately following the end of infusion (15 ± 5 minutes).

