9.6 Study Drug Administration

Specific instructions on administration and supplies required for administration are detailed in the Pharmacy Manual. In general, study drug will be infused through a peripheral vein intravenous set. The intravenous line may be kept open before and after the infusion with sufficient quantities of 0.9% NaCl to assure patency, as needed.

A volume of 100 mL* of the calculated dose of study drug will be infused over at least 4 hours on Extension Day 1, over at least 3 hours on Extension Day 29, and over 1 to 4 hours thereafter, depending on the patient's tolerance of the previous infusions and at the Investigator's discretion. If the infusion is slowed or interrupted, the time may be extended longer than 4 hours, as long as it does not exceed 8 hours.

- * Due to the rounding of the total infusion volume by some programmable infusion pumps, an infusion of 99 to 101 mL will be considered a complete infusion and will not be recorded as a deviation of the study.

Prior to first infusion of AK002, patients will be premedicated with 60 mg oral prednisone (or approved equivalent) 12–24 hours prior to the start of the study drug infusion. For subsequent infusions, premedication may be used at the discretion of the Investigator, for patient tolerability, and with approval from the Medical Monitor. An alternate premedication regimen may be used with the approval of the Medical Monitor.

The intravenous infusion may be interrupted and/or the rate may be reduced if a patient has an IRR. The time that the infusion is initiated/concluded (including any interruptions) will be documented in the eCRF. If the infusion is restarted after an interruption, the infusion must be completed within 8 hours of preparation. Administration will be discontinued if, in the opinion of the Investigator, an interrupted infusion cannot be restarted for safety reasons or if the infusion cannot be completed within 8 hours of preparation. Administration will also be discontinued in any patient experiencing a serious adverse event during the course of the infusion.

The patient will be observed for 4 hours after the end of the first infusion and if no issues are noted, will be observed for at least 1 hour for subsequent infusions, as per Investigator discretion and depending on tolerance to prior infusions.

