11.3.4 Vital Signs

Vital signs, including systolic and diastolic blood pressure, pulse, body temperature, and respiratory rate, will be taken after the patient has been at rest for ≥ 5 minutes and before any blood draw (except post-infusion for which vital signs will be obtained as described below).

On dosing days, vital signs will be measured pre-dose, 15 (± 5) minutes after the start of infusion, and immediately following the end of infusion (+5 minutes). Please refer to the schedule of assessments in [Table 1](#).

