12.2 Extension Day 1 – First Day of Dosing

The following procedures will be performed prior to study drug infusion:

- Confirm eligibility for the study.
- Obtain the SF-36 Health Survey from the Day 113 visit of Study AK002-003 or newly collected for patients that were discontinued from study treatment due to high eosinophil counts or are >45 days from their Day 113 visit in AK002-003.
- Determine body weight: Obtain from the Day 113 visit of Study AK002-003 if Day 113 is the same day or day prior to Extension Day 1. If Day 113 of Study AK002-003 is more than 1 day prior to Extension Day 1, a new body weight must be obtained.
- Enter PID and weight into IRT.
- Document any changes in baseline diet: Obtain from Day 113 visit of Study AK002-003 or newly collected for patients that were discontinued from study treatment due to high eosinophil counts or are >45 days from their Day 113 visit in AK002-003.
- Collect vital signs: Obtain from Day 113 visit of Study AK002-003 or newly collected for patients that were discontinued from study treatment due to high eosinophil counts or are >45 days from their Day 113 visit in AK002-003.
- Perform symptom-directed physical examination, as needed: Obtain from Day 113 visit of Study AK002-003 or newly collected for patients that were discontinued from study treatment due to high eosinophil counts or are >45 days from their Day 113 visit in AK002-003.
- Collect blood samples for CBC, blood chemistry, ADA, and PK if not collected at the Day 113 visit of Study AK002-003 or for patients that were discontinued from study treatment due to high eosinophil counts or are >45 days from their Day 113 visit in AK002-003. Differential cell counts from Day 113 in AK002-003 will remain blinded.
- Collect urine for urinalysis: Obtain from the Day 113 visit of Study AK002-003 or newly collected for patients that were discontinued from study treatment due to high eosinophil counts or are >45 days from their Day 113 visit in AK002-003.
- Collect urine and perform urine pregnancy test if patient is of childbearing potential.
- The study pharmacist will prepare study drug at 1 mg/kg using the body weight obtained at the visit. The final combined volume of the intravenous bag of study drug + 0.9% NaCl will be 120 mL.

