15.3 Demographic and Baseline Characteristics

The following demographic and baseline variables will be summarized:

- Demographics
- Extension Day 1 predose vital signs and laboratory tests

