15.5 Analysis of Safety Endpoints

Adverse Events: All AE will be coded using the Medical Dictionary for Regulatory Activities (MedDRA) and will be classified by MedDRA system organ class and preferred term. Listings will include all AE collected on study. The summaries of AE will be based on TEAE, defined as an AE reported in the clinical database with a date of onset (or worsening) on or after the start date of the first intravenous infusion of the study medication.

Patient incidence (N and %) of TEAEs will be summarized as follows:

- Overview of TEAE to include
 - Number (%) of patients who report at least 1 TEAE overall, by severity and by relationship
 - Number (%) of patients who report at least 1 serious TEAE
 - Number (%) of patients who report at least 1 TEAE leading to treatment discontinuation
 - Number (%) of patients who report at least 1 TEAE of special interest
- TEAE by preferred term
- TEAE by system organ class and preferred term
- TEAE by maximum severity, system organ class, and preferred term
- Drug-related TEAE by system organ class and preferred term
- TEAE leading to withdrawal by system organ class and preferred term
- Serious TEAE by system organ class and preferred term
- TEAE of special interest by system organ class and preferred term

Clinical Laboratory Assessments: Samples will be obtained for the clinical laboratory tests identified in Section 11.4, and laboratory tests to be summarized include blood chemistry, hematology, urinalysis, and ADA.

Descriptive statistics will be used to summarize laboratory results at baseline, each visit, and the change from baseline for each visit. In addition, shift tables will summarize the laboratory results relative to normal reference ranges at baseline and each post-baseline time point.

Vital Signs: Vital signs will be summarized at baseline, each visit, and change from baseline at each visit.

Physical Examination: New or worsening symptoms in the symptom-directed physical examinations will be included in the by-patient data listings.

Concomitant Medications: All medications will be coded using the most current World Health Organization Drug Dictionary. Concomitant medications will be summarized by Anatomical Therapeutic Chemical Class and preferred term.

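### Observation after the first extension infusion is 4 hours in Section 9.6, 1 to 4 hours in Section 12.2 and 1 hour in the Synopsis; a same-day pre-dose vital-sign reading is also worth adding.

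*Combined protocol and SAP*

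**What the plan says.** **Observation.** Section 9.6 sets 4 hours after the first infusion and, if that goes without problems, at least 1 hour after later ones. Section 12.2, the procedure list for Extension Day 1, gives a range of 1 to 4 hours. The Synopsis entry on test product and administration gives 1 hour and does not say which infusion it means.

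**Vital signs.** The general rule is in Table 1 note 5, "Vital signs will be measured on all dosing days pre-dose", and in Section 11.3.4, "On dosing days, vital signs will be measured pre-dose". The Day 1 vital-signs cell of Table 1 carries superscript 4, and that note begins "Do not collect if procedure was performed" and applies to procedures done up to 45 days before Extension Day 1. Section 12.2 spells out the same rule: "Collect vital signs: Obtain from Day 113 visit of Study AK002-003 or newly collected", with new collection only for patients stopped for high eosinophil counts or more than 45 days past Day 113. For body weight the same section is stricter: "If Day 113 of Study AK002-003 is more than 1 day prior to Extension Day 1, a new body weight must be obtained".

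**Analysis.** Section 15.3 lists "Extension Day 1 predose vital signs and laboratory tests" among the baseline variables. Section 15.5 adds: "Vital signs will be summarized at baseline, each visit, and change from baseline at each visit". Section 15 plans no formal inference.

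**The concern.** The protocol treats the first infusion as the riskier one. Section 2.3 reports fewer adverse events at the second and later infusions than at the first, names infusion-related reactions as the most common treatment-emergent event, and counts two of them as serious. Section 9.6 is the only place that turns this into a longer watch. A site that follows the visit list can stop at 1 hour, comply with 12.2 and breach 9.6. Section 16.4 requires decisions on all protocol violations before database lock, and the two sections give no common rule for whether a 1-hour release is one.

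The vital-signs exception bears on the same infusion. The readings at 15 minutes and at the end of the infusion are most useful against a value taken shortly before it. Hypotension, hypertension and fever are among the reaction symptoms listed in Section 13.4, and reduced blood pressure is one of the anaphylaxis criteria in Appendix 19.4. A completer who starts some weeks after Day 113 may have no such same-day value. The older value then also serves as the vital-sign baseline.

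**Working it through.** **1. Observation times side by side**

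| Place | Infusion | Time after end of infusion |
|---|---|---|
| Section 9.6 | First | 4 h |
| Section 9.6 | Later | at least 1 h |
| Section 12.2 | First | 1 to 4 h |
| Section 12.3 | Second | at least 1 h |
| Section 12.6 | 9 to 20 | 1 to 4 h |
| Synopsis | Not named | 1 h |

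The largest shortfall at the first infusion is 4 h − 1 h = 3 h. The minimum in 12.2 equals that for the second infusion, and its wording matches that for infusions 9 to 20. The visit lists therefore set no longer minimum for the first infusion.

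**2. Patients for whom this is first exposure to AK002**

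Inputs: 65 randomized 1:1:1 in the parent study (Section 2.3) and about 60 expected to enter (Section 15.1). Assumptions: balanced allocation, so 21 or 22 on placebo; and 55 to 65 entrants. The lower bound takes every non-entrant from a placebo group of 21; the upper bound takes none from a group of 22.

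- 55 enter: 65 − 55 = 10 non-entrants, so 21 − 10 = 11 up to 22.
- 60 enter: 65 − 60 = 5 non-entrants, so 21 − 5 = 16 up to 22.
- 65 enter: 21 or 22.

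These are ex-placebo entrants, not patients known to have been released early.

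**3. Vital signs by start time**

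- Same day as Day 113, the default in the Synopsis: the Day 113 reading is the Day 1 reading, so nothing is missing.
- 1 to 45 days after Day 113: no new reading is required. From 2 days on, the carried-over value also predates the premedication in Section 9.6 ("patients will be premedicated with 60 mg oral prednisone"), which is given 12 to 24 hours before the infusion.
- More than 45 days after, or stopped for high eosinophil counts: a new reading is required.

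**4. Is note 4 a considered rule for every cell that carries it?**

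Table 1 also puts superscript 4 on the Day 1 cells for body weight and the pregnancy test. Section 12.2 overrides it in both: weight may be at most 1 day old, and the pregnancy test has no carry-over option. The superscript is therefore applied too broadly in at least two other rows. For vital signs, however, 12.2 agrees with it.

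**5. Reach of a carried-over baseline**

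Doses fall on days 1 + 28 × (0 to 25), that is 26 doses, the last on Day 701. After Day 1 there are 25 dosing visits and 3 follow-up visits with vital signs in Table 1 (Days 736, 757 and 785), so 25 + 3 = 28 scheduled changes from baseline per affected patient. If Section 12.12 is followed, which lists no vital signs at the last two visits, the count is 25 + 1 = 26. These counts repeat one baseline issue; they are not 28 separate problems.

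**The case against.** **On vital signs**, a reader might infer that 12.2 contradicts note 5 and Section 11.3.4. The documents do not support that. Note 4 sits on the very cell in question, 12.2 states the same 45-day rule in full, and 11.3.4 closes by referring to Table 1. The same threshold is applied in 12.2 to the SF-36, diet, physical examination, blood samples and urinalysis. Nor does the label in Section 15.3 show that same-day values were intended: Section 6.2 describes pharmacokinetic samples as predose on Extension Day 1 while taking them from the Day 113 visit. The body-weight comparison is limited too, since weight sets the dose and vital signs do not. All of this stands. What it leaves untouched is the clinical gap: read as a deliberate exception, the rule still permits an infusion with no same-day reading before it.

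**On observation**, the 4 hours of Section 9.6 lie inside the range in 12.2, so a site that follows 9.6 satisfies both. That is correct, but the converse fails, and 12.2 is the list a site works from on the day.

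**On weight**, Section 2.3 compares first with later AK002 infusions, and about two thirds of parent-study patients had been assigned AK002, so for them this is not a first exposure. The prednisone, the infusion over at least 4 hours, the blood count 1 hour after the end, the 24-hour capture of infusion-related reactions and the emergency equipment are all unaffected. By Amendment 7 the parent study had been fully enrolled and reported, and completers start on or about Day 113, so few first infusions may remain. These points stand and keep the severity low.

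**Conclusion.** The observation time is wrong as written. Three places give three figures, and at the first infusion the gap between 12.2 and 9.6 is up to 3 hours. It matters most for ex-placebo patients: 11 to 22 of them under the stated assumptions, or 16 to 22 if exactly 60 enter.

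The vital-signs rule is a coherent exception that is worth narrowing. It concerns only completers who start 1 to 45 days after Day 113, and their number is not stated.

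A reader might go further and infer that patients were released early, or that the vital-sign results are biased. Nothing in the documents shows either. The effect on the analysis is one of labelling: a carried-over value would serve as the reference in descriptive summaries. The separate SAP that Section 15 refers to is not included in the document reviewed and may already deal with it.

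Severity is minor. If no first infusions remain, the baseline flag and the question of what counts as a deviation are what is left in practice; the rest is a wording correction.

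**What to change.** 1. State 4 hours after the first infusion in Section 12.2 and in the Synopsis, as in Section 9.6, and keep at least 1 hour for later infusions. Cost: wording in the next amendment and up to 3 more hours of observation at one visit.
2. Remove superscript 4 from the Day 1 vital-signs cell in Table 1, and amend 12.2 to require new pre-dose vital signs on Extension Day 1 unless the Day 113 visit is the same day. Cost: one extra set of vital signs for later starters, with no added blood draw and no unblinding.
3. For patients already dosed without same-day vital signs, flag the carried-over baseline in the vital-sign listing and give its age in days. Cost: one flag in one listing.

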12.3 Extension Day 29 (± 3)

The following procedures will be performed prior to study drug infusion:

- Have patient complete the SF-36 Health Survey.
- Have patient complete PGIC Questionnaire.
- Determine body weight.
- Enter PID and weight into IRT.
- Document any changes in diet from last study visit.
- Collect vital signs.
- Collect urine and perform urine pregnancy test if patient is of childbearing potential.
- Perform symptom-directed physical examination, as needed.
- Collect blood samples for CBC, blood chemistry and ADA.
- The study pharmacist will prepare study drug at 3 mg/kg using the body weight obtained at the visit. The final combined volume of the intravenous bag of study drug + 0.9% NaCl will be 120 mL.

Procedures associated with the infusion of study drug include:

- Premedication may be administered at the Investigator's discretion, in discussion with the Medical Monitor for the Day 29 infusion.
- Infuse 100 mL of study drug using an infusion pump over 3 hours on Extension Day 29. See Pharmacy Manual for Infusion Rates. Record the start and stop times of the infusion including any times the infusion is interrupted.

The following procedures will be performed after study drug infusion:

- Collect vital signs immediately following (+5 minutes) the end of infusion.
- Collect CBC with differential 1 hour (± 15 minutes) after the end of infusion.
- Observe the patient for at least 1 hour after the end of infusion.

Concomitant medication use and AE (including AESI and SAE) will be documented throughout the clinic visit.

12.4 Extension Day 57 (± 3) to Extension Day 197 (± 3)

The following procedures will be performed on Extension Days 57, 85, 113, 141, 169, and 197 (± 3 days).

The following procedures will be performed prior to study drug infusion:

- Have patient complete the PGIC questionnaire on Extension Day 57 and Day 85 only.
- Have patient complete the SF-36 Health Survey.
- Determine body weight.
- Enter PID and weight into IRT.
- Document any changes in diet.
- Collect vital signs.
- Collect urine and perform urine pregnancy test if patient is of childbearing potential.
- Perform symptom-directed physical examination, as needed.
- Collect blood samples for CBC, blood chemistry and ADA.
- The study pharmacist will prepare study drug at 3 mg/kg using the weight obtained at the visit.

Procedures associated with the infusion of study drug include:

- Premedication may be administered at the Investigator's discretion, in discussion with the Medical Monitor for Day 57–Day 197 infusions.
- Infuse 100 mL of study drug using an infusion pump over at least 1 to 4 hours, depending on Investigator's discretion and tolerance to prior infusions. See Pharmacy Manual for Infusion Rates. Record the start and stop times of the infusion including any times the infusion is interrupted.
- Collect vital signs 15 (± 5) minutes after the start of infusion.
- An unscheduled ADA blood sample may be obtained if an immunogenicity-related AE is suspected.

The following procedures will be performed after study drug infusion:

- Collect vital signs immediately following (+5 minutes) the end of infusion.
- Collect CBC with differential 1 hour (± 15 minutes) after the end of infusion.
- Observe the patient for at least 1 hour after the end of each infusion.

Concomitant medication use and AE (including AESI and SAE) will be documented throughout the clinic visit.

12.5 Extension Day 211 (± 3)

All risks and associated details regarding the EGD procedure will be discussed with the patient by the EGD provider.

- Patient should arrive fasting for the EGD procedure, as specified by instructions from the EGD provider.
- Collect AE, SAE, and changes in concomitant medications. Capture all concomitant medications provided to the patient during the EGD.
- Perform the EGD with biopsy following procedures provided by Allakos and all EGD facility SOPs.

12.6 Extension Day 225 (± 3) to Extension Day 533 (± 3)

The following procedures will be performed on Extension Days 225, 253, 281, 309, 337, 365, 393, 421, 449, 477, 505, and 533 (± 3 days).

The following procedures will be performed prior to study drug infusion:

- Have patient complete the SF-36 Health Survey.
- Determine body weight.
- Enter PID and weight into IRT.
- Document any changes in diet.
- Collect vital signs.
- Perform urine pregnancy test if patient is of childbearing potential.
- Perform symptom-directed physical examination, as needed.
- Collect blood samples for CBC, blood chemistry, and ADA. ADA should only be collected on dosing days through Extension Day 365 and on Extension Day 533.
- The study pharmacist will prepare study drug at 3 mg/kg using the weight obtained at the visit.

Procedures associated with the infusion of study drug include:

- Premedication may be administered at the Investigator's discretion, in discussion with the Medical Monitor.
- Infuse 100 mL of study drug using an infusion pump over at least 1 to 4 hours, depending on Investigator discretion and tolerance to prior infusions. See Pharmacy Manual for Infusion Rates. Record the start and stop times of the infusion including any times the infusion is interrupted.
- Collect vital signs 15 (± 5) minutes after the start of infusion.
- An unscheduled ADA blood sample may be obtained if an immunogenicity-related AE is suspected.

The following procedures will be performed after study drug infusion:

- Collect vital signs immediately following (+5 minutes) the end of infusion.
- Collect CBC with differential 1 hour (± 15 minutes) after the end of infusion.
- Observe the patient for 1 to 4 hours after the end of infusion.

Concomitant medication use and AE (including AESI and SAE) will be documented throughout the clinic visit.

